2.3. Clinical Studies

The clinical development program for tafenoquine has spanned decades and consists of 16 Phase 1, nine Phase 2 and two Phase 3 clinical studies in more than 4,000 participants. The studies have included single and multiple oral dose studies, single dose rising studies in fasted and non-fasted participants, bioavailability studies for different tafenoquine formulations, drug-interaction and safety studies and malaria challenge studies. Field studies to assess tafenoquine efficacy have been conducted in Africa and Asia (60P IB).

2.3.1. Efficacy

Phase 1 malaria challenge studies and Phase 2 and 3 clinical studies with tafenoquine have shown the potential utility of tafenoquine in the chemoprophylaxis of *P. falciparum* and *P. vivax* malaria (reflecting activity against initial liver forms and blood asexual forms) and in the radical cure/relapse prevention in *P. vivax* infection (reflecting activity against liver hypnozoites). Tafenoquine also has anti-gametocidal activity (Study 058).

Tafenoquine has been assessed for its ability to treat existing infection with *P. vivax*. Parasitemia (parasites/ μ L) was recorded on Day 0 (the day treatment was started) as well as on Days 1 and 2 after treatment was started. In 43 patients, mean (highest) parasitemia values were: 8000 (44000) and 8000 (49000) for AM and PM on Day 0; 6000 (2000) and 5000 (16000) for AM and PM on Day 1; 3000 (12000) and 2000 (10000) for AM and PM on Day 2. For a randomized group of 22 patients administered standard therapy with chloroquine/primaquine, values were: 6000 (30000) and 8000 (40000) for AM and PM on Day 0; 2000 (4000) and 1000 (12000) for AM and PM on Day 1; 100 (500) and 100 (100) for AM and PM on Day 2. These data indicate that for treatment of *P. vivax*, the decline of parasitemia with time is slower for tafenoquine than for a standard blood schizonticide such as chloroquine, but this observation is of little consequence for chemoprophylactic use of the drug as a monotherapy (Study 058).

Pivotal trials in Oceania and in Africa have shown tafenoquine to have the same prophylactic efficacy as mefloquine. For non-immunes in Oceania where the incidence of *P. falciparum* and *P. vivax* malaria in non-chemoprophylaxed persons was estimated to be 1% and 7% respectively, the prophylactic efficacies of weekly tafenoquine and mefloquine were both 100% (Dow 2014). For semi-immunes in Africa where the incidence of *P. falciparum* infection in placebos was measured as 32%; the number of persons infected in the weekly tafenoquine and mefloquine groups were each 2% (Dow 2015).

2.3.2. Human Safety Data

Tafenoquine has been evaluated in over 4,000 healthy volunteers and patients with malaria in Phase 1, Phase 2, and Phase 3 clinical studies including single and multiple oral dose studies, dose rising studies in fasted and non-fasted participants, bioavailability studies for different tafenoquine formulations, drug-interaction studies, malaria challenge studies, malaria prophylaxis and *P. vivax* malaria treatment studies. In the studies conducted to date, a capsule formulation containing dosage strengths of 4 mg, 14 mg, 25 mg, 50 mg, 100 mg, 200 mg and 250 mg of tafenoquine (as tafenoquine succinate) was studied. Undesirable effects in this large sample of participants and patients administered multiple doses can be summarized as the following and are presented in Table 3:

- Blood and lymphatic system disorders, including hemolytic anemia (in patients with G6PD deficiency) and methemoglobinemia.
- Corneal deposits that are fully reversible (within 1 year). Notably, no treatment-related retinal findings were observed following extended treatment (200 mg x 3 days loading dose followed by 200 mg/week for 23 weeks) in a Phase 1 clinical safety study (Leary 2009; Study 057).
- GI disorders: nausea, vomiting, abdominal pain and diarrhea.
- Immune system disorders: hypersensitivity reactions including urticaria.

Table 3: Adverse Events occurring in $\geq 1\%$ of Subjects in the Tafenoquine ACR Group and with an Incidence Numerically Greater than in the Placebo Group

Adverse Reaction	All Tafenoquine Subjects (N=825)	Non-Deployed Tafenoquine Subjects (N=333)	Placebo (N=396)
Gastroenteritis	209 (25.3%)	26 (7.8%)	17 (4.3%)
Back pain	116 (14.1%)	47 (14.1%)	26 (6.6%)
Nasopharyngitis	108 (13.1%)	11 (3.3%)	9 (2.3%)
Diarrhea	105 (12.7%)	16 (4.8%)	23 (5.8%)
Keratopathy*	68 (8.2%)	0	0
Soft tissue injury	62 (7.5%)	2 (0.6%)	0
Arthralgia	61 (7.4%)	14 (4.2%)	15 (3.8%)
Heat rash	53 (6.4%)	0	0
Viral infection	48 (5.8%)	8 (2.4%)	6 (1.5%)
Laceration	37 (4.5%)	8 (2.4%)	6 (1.5%)

Table 3: Adverse Events occurring in $\geq 1\%$ of Subjects in the Tafenoquine ACR Group and with an Incidence Numerically Greater than in the Placebo Group (Continued)

Adverse Reaction	All Tafenoquine Subjects (N=825)	Non-Deployed Tafenoquine Subjects (N=333)	Placebo (N=396)
Vomiting	31 (3.8%)	7 (2.1%)	6 (1.5%)
Oropharyngeal pain	30 (3.6%)	18 (5.4%)	12 (3.0%)
Tonsillitis	27 (3.3%)	11 (3.3%)	2 (0.5%)
Rash	25 (3.0%)	5 (1.5%)	2 (0.5%)
Tinea pedis	24 (2.9%)	0	0
Lethargy	24 (2.9%)	1 (0.3%)	0
Motion sickness	21 (2.5%)	0	0
Joint injury	21 (2.5%)	3 (0.9%)	0
Seasonal allergy	20 (2.4%)	1 (0.3%)	0
Chest pain	18 (2.2%)	17 (5.1%)	5 (1.3%)
Body tinea	17 (2.1%)	5 (1.5%)	4 (1.0%)
Sinusitis	17 (2.1%)	5 (1.5%)	2 (0.5%)
Muscle strain	17 (2.1%)	3 (0.9%)	2 (0.5%)
Neck pain	17 (2.1%)	5 (1.5%)	4 (1.0%)
GERD	14 (1.7%)	1 (0.3%)	1 (0.3%)
Arthropod bite	14 (1.7%)	2 (0.6%)	2 (0.5%)
Ingrowing nail	12 (1.5%)	0	0
Ear pain	11 (1.3%)	5 (1.5%)	4 (1.0%)
Otitis externa	11 (1.3%)	2 (0.6%)	4 (1.0%)
Heat illness	11 (1.3%)	0	0
Ligament sprain	10 (1.2%)	4 (1.2%)	0
Thermal burn	10 (1.2%)	1 (0.3%)	0
Insomnia	10 (1.2%)	2 (0.6%)	3 (0.8%)
Impetigo	8 (1.0%)	0	0
Tinea infection	9 (1.1%)	2 (0.6%)	0

*Early reports of corneal deposits thought to be secondary to phospholipidosis were initially reported as keratopathy and reported as SAEs. Once these were determined to be benign and reversible, later reports of keratopathy were not reported as SAEs.

2.3.3. Human Pharmacokinetic Data

In PK studies in humans, AUC and maximum concentration (C_{\max}) of tafenoquine increased in a dose proportional fashion, and the mean terminal half-life ($t_{1/2}$) of tafenoquine ranged from 13 to 15 days. Food can increase the absorption of tafenoquine, as AUC and C_{\max} increased 41% and 31%, respectively, when the drug was administered with a high fat meal

compared with dosing in the fasted state. However, tafenoquine can be taken with or without food at the recommended dose to produce therapeutic blood levels, so there are no dietary restrictions.

Population PK analysis showed that tafenoquine typical values of the first-order absorption rate constant (k_a), clearance (CL/f) and volume of distribution (V/f) were 0.243 h^{-1} , 0.056 L/h/kg and 23.7 L/kg , respectively, and the mean elimination $t_{1/2}$ was 12.7 days. Only body weight had a significant effect on V/f and CL/f, both increasing with increasing weight (60P IB).

3. STUDY RATIONALE

Previous studies in over 4,000 healthy volunteers and patients suggests tafenoquine is safe and efficacious when given over a period of 6 months.

This study will evaluate the overall safety and tolerability of tafenoquine for long-term use (12-months). Participation in the study will be approximately 80 weeks, including a screening period of up to 4 weeks, a 52 week dosing period (including the loading dose in Week 1), and a 24-week follow-up period.

This study aims to expand the safety database for tafenoquine for a 12-month period of exposure by examining general tolerance and detailed assessments of ophthalmologic parameters, clinical laboratory tests, and psychiatric evaluation to support the use of tafenoquine as a potential antimalarial prophylactic drug to prevent malaria in adults for longer term use. Specifically, ophthalmologic changes will be assessed from Screening using SD-OCT (including wide field macular scan) and qFAF at Weeks 12, 24, 52, and 64 (Visits 4, 5, 6, and 7), and if required also at Weeks 76, 89 and 104 (Visits 8, 9 and 10) in healthy (G6PD normal) adult participants, dosed with tafenoquine 200 mg once a day (QD) for 3 days and then 200 mg every week up to 51 weeks. Additional ophthalmic assessments will include BCVA using the ETDRS chart, FM-100 hue test, Mars letter contrast sensitivity test, M-chart, slit lamp evaluations of the corneal epithelium, microperimetry and retinal digital photography (conventional and wide field, to enable detection of subtle peripheral toxicity). The incidence, severity and relationship to tafenoquine of AEs (unexpected toxicities, AEs encountered during or after tafenoquine administration), safety laboratory parameters, and vital signs and ECG up to and including Week 64 (Visit 7) at a $\geq 1\%$ (common) or $\geq 10\%$ very common frequency. A placebo control group will be used to compare the results in the tafenoquine group.

While neurologic and psychiatric events are rare, neurologic and psychiatric AEs have been reported in clinical trials conducted with tafenoquine and mefloquine. The AEs reported in the treatment group were: abnormal dreams, sleep disorders, nightmares, depression, agitation, anxiety disorder, euphoric mood, bipolar disorder, depressed mood, neurosis, panic attack, stress, and suicide attempt.

This study will continue the characterization of the exposure-response relationship for these AEs including sleep disturbances assessed using the LSEQ and the development of psychiatric disorders in accordance with DSM-5 criteria using the M.I.N.I. English Version 7.0.2 and suicidality using the C-SSRS. The DHI will be used to assess severity of dizziness as it relates particularly to effects on functioning, if dizziness or vertigo is reported as an AE.

4. STUDY OBJECTIVES

4.1. Primary Objective

To assess the long-term ophthalmic safety of tafenoquine Recommended Regimen after 12 months of exposure versus placebo using SD-OCT and qFAF.

4.2. Secondary Objectives

To assess the long-term safety and tolerability of tafenoquine versus placebo as assessed by clinical monitoring of vital signs, ECG, laboratory data, and reporting of AEs after 12 months of exposure.

To assess the long term safety and tolerability of tafenoquine after 12 months of exposure to tafenoquine versus placebo by measuring ophthalmic and psychiatric changes from baseline to end of study.

5. STUDY DESIGN

5.1. Overview

This randomized, double-blind, placebo controlled study will involve 600 healthy (G6PD normal) volunteers and will run in three parts. The Study Site may stagger enrollment of participants into weekly groups to accommodate the screening period.

Part 1 – Treatment phase (52 weeks)

Participants who meet the eligibility criteria will be randomized (ratio 1:1) using clinical site as a randomization variable to receive a loading dose of either tafenoquine 200 mg (2 x 100 mg tablets) or placebo daily for 3 consecutive days starting at Day 1, Week 1 (Visit 2), followed by study treatment (tafenoquine 200 mg or placebo) once per week for 51 weeks with safety follow-up visits at Weeks 4, 12, 24 and 52 (Visits 3, 4, 5, and 6). All efforts will be made to retain participants through to study completion. The reasons for withdrawal may include: 1) withdrawal of consent, 2) lost to follow-up, 3) evidence of substance abuse that may affect the participant's capacity to complete the study in the investigator's opinion, and 4) development of a new or worsening psychiatric disease (including suicidal ideation) at a non-scheduled visit or during routine M.I.N.I. evaluation that would jeopardize the safety of the participant if they continued in the study (see [Section 9.2.7](#)). If a participant stops taking their study drug, they should continue to have all follow-up safety visits. If the subject wants to withdraw, they should have an EOS visit (preferably 65-75 days after cessation of study treatment that includes all of the Week 64 assessments). The reasons for any treatment discontinuation (temporarily or permanently) will be documented on the eCRF.

Part 2 – Follow-up phase (12 weeks)

Due to the long t_{1/2} of tafenoquine (13-15 days with an expected 65-75-day washout period), all participants will return to the clinic at the Week 64 (Visit 7a and 7b) for their EOS visit. If the participant has an ongoing AE, they will continue in Part 3 of the study, otherwise this is the final visit.

Part 3 – Follow-up Phase (every 12 weeks, up to 12 months)

Participants who meet the criteria for continuation for additional safety assessments at Week 64 (Visit 7a and 7b) will continue to be assessed for up to 3 more times at approximately 12-week intervals or until resolution or stabilization of the AE whichever is earlier.

The duration of subject's participation in the study will be up to 110 weeks, including a screening period of up to 6 weeks, a 52-week dosing period, and a 12-week follow-up period. If abnormalities are detected at the 12-week follow-up visit (Week 64 EOS) the subject will continue quarterly follow-up out to 12 months post last dose of IMP. For example, if corneal deposit was the only abnormality found during Week 64, then there is no need to repeat any of the ocular examinations except for corneal photography and corneal slit lamp examination at Weeks 76, 89 or 104 (Visits 8, 9 or 10).

The study will consist of the following for each participant:

- A screening period of up to 6 weeks prior to the first IMP dose. At the first screening visit (Visit 1a), subjects will be screened for eligibility with the exception of the

ophthalmologic assessments. If still eligible after the first visit, the subject will be scheduled for screening and baseline ophthalmic testing (Visit 1b).

- Randomization to receive tafenoquine or placebo in a 1:1 ratio using clinical site as a randomization variable;
- One 200 mg dose of tafenoquine per day for three consecutive days (loading doses; Days 1, 2 and 3) (Week 1, Visit 2) or equivalent dose of matched placebo;
- Once weekly 200 mg doses of tafenoquine or equivalent placebo on Week 2 through Week 52; Follow-up visits on Weeks 4, 12, 24, 52 and 64, and if applicable, Weeks 76, 89, and 104 to follow any ongoing AEs from the prior visit.

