	
Orlando system).
 
 • After pupil dilation: 
 ○ MAIA microperimetry; ○ Heidelberg Spectralis SD-OCT (including wide field macula scan); ○ Heidelberg Spectralis qFAF (set of 3 images to ensure consistency in measurement); ○ Digital photograph of corneal surface (conventional and wide field); ○ Digital photograph of retina (conventional and wide field); ○ Slit lamp retinal examination and IOP measurement; and • Psychiatric Assessments: 
 ○ M.I.N.I. English Version 7.0.2 at Weeks 12, 24 and 52; ○ DHI (only collected if participant reports AE of dizziness or vertigo); ○ LSEQ; and, ○ C-SSRS – every 4 weeks \pm 1 week after the Week 52 Visit • AEs. 
Part 3 - Follow-up Ongoing AEs Weeks 76, 89, and 104 (Visits 8, 9 and 10) every 3 months until resolution (out to 12 months post final study drug dose – visits will only be scheduled if an AE was ongoing at a prior visit):
 
 • 12-lead ECG • Blood sampling. 
 • CBC and biochemistry; and • MetHb%. • Urinalysis (specific gravity, pH, glucose, protein, blood, ketones, leukocyte esterase, and nitrites). Microscopic examination (if blood, leukocyte esterase or nitrites are positive). • Ophthalmic assessments, including selected ophthalmic examination, microperimetry, BCVA (EDTRS), FM-100 hue testing, Mars letter contrast sensitivity test, M-chart and qFAF to follow only specific, abnormal results. • Psychiatric assessments: 
 ○ M.I.N.I. English Version 7.0.2. (If required to follow-up an AE or disorder). ○ DHI (if AE reported by participant); and • Any other AE. 
For compliance confirmation during the dosage phase – plasma samples will be taken at Weeks 1, 4, 12, 24, and 52. There is no specific timing for obtaining the pharmacokinetic (PK) sample during each scheduled visit. The date and time of the PK sample is to be recorded in the eCRF. Date, time, and number of tablets recorded in participant diary cards and/or electronic compliance management system will also be transferred to the eCRF.
 
Drawing of blood samples is estimated to be 135 mL/participant within the trial prescribed procedures and will not exceed 275 mL for the entire study period (Appendix 3).

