1. STUDY SCHEDULE OF EVENTS

Study Phase	Screening		Treatment (Week 1 to Week 52)					Phase 2 Follow-up	Phase 3 follow-up (ongoing AEs at end of Phase 2)		
Week	-6 Weeks to Day -1		Week 1, Day 1	Week 4 ±3 days	Week 12 ±2 weeks	Week 24 ±2 weeks	Week 52 ± 2 weeks	Week 64 ±2 weeks (EOS)	Week 76 ± 2 weeks	Week 89 ± 2 weeks	Week 104 ± 2 weeks
Visit Number	1a/ 1b ^a		2	3	4	5	6	7a/7b ^b	8	9	10
Written informed consent	X		X ^c								
Randomization			X								
Inclusion & exclusion	X		X								
Demographics	X										
Body height and weight	X										
Medical, surgical & social history	X		Update								
Prior medications ^d	X		Update								
Physical examination ^e	X		X	X	X	X	X	X			
Vital signs ^f	X		X	X	X	X	X	X			
12-lead ECG	X			X			X	X	Repeat if needed to follow AE		
Hematology/ biochemistry ^g	X		X	X	X	X	X	X	Repeat if needed to follow AE		
G6PD testing	X										
Methemoglobin (MetHb%)	X		X	X	X	X	X	X	Repeat as needed to follow AE		
Serology ^h	X										
Pregnancy test ⁱ	X		X	X	X	X	X	X			
PK blood collection for tafenoquine ^j			X	X	X	X	X				

Study Phase	Screening		Treatment (Week 1 to Week 52)					Phase 2 Follow-up		Phase 3 follow-up (ongoing AEs at end of Phase 2)		
Week	-6 Weeks to Day -1		Week 1, Day 1	Week 4 ±3 days	Week 12 ±2 weeks	Week 24 ±2 weeks	Week 52 ± 2 weeks	Week 64 ±2 weeks (EOS)		Week 76 ± 2 weeks	Week 89 ± 2 weeks	Week 104 ± 2 weeks
Visit Number	1a/ 1b ^a		2	3	4	5	6	7a/7b ^b		8	9	10
Alcohol breath test	X		X									
Urinalysis (dipstick) and urine drug screen ^k	X		X	X	X	X	X	X		Repeat urinalysis only if needed to follow AE		
Ophthalmic assessments (before dilation: BCVA (ETDRS letter score FM-100 hue test, MARS letter contrast sensitivity test, M-Chart and slit lamp examination/grading of deposits after Screening. (After dilation: SD-OCT, qFAF, digital photograph of cornea, retina (conventional and wide field), slit lamp retinal exam and IOP measurement		X			X	X	X		X	Repeat if needed to follow AE		
Microperimetry ^l		X				X	X		X	Repeat if needed to follow AE		
MINI 7.0.2	X				X	X	X	X		Repeat if needed to follow AE		
DHI			Only collected if participant reports AE of dizziness or vertigo							Repeat if needed to follow AE		
LSEQ			X	X	X	X	X	X				
C-SSRS			X	Every 4 weeks ± 1 week								
AE collection			X	X	X	X	X	X		Repeat if needed to follow AE		
Concomitant medication			X	X	X	X	X	X				
IMP administration			200 mg daily x 3 days Week 1, then 200 mg once/week through to Week 52									

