5.2.2. Secondary Endpoints

- The incidence, severity and relationship to the IMP of AEs (including unexpected toxicities, AEs encountered during or after IMP administration), safety laboratory parameters, vital signs, and ECG up to and including the end of treatment period Week 52 (Visit 6).
- Mean change from baseline in key SD-OCT parameters including CST, TMV, parafoveal (inner ring of ETDRS grid) retinal thickness and the proportion of participants ellipsoid and interdigitating zone disruption (as per [Table 5](#)).
- Proportion of participants with abnormal changes from baseline observed on qFAF using the Spectralis HRA+OCT device with grey scale values extracted from these images for statistical analysis using qFAF software (Heidelberg Engineering).
- Mean change from baseline in BCVA.
- Proportion of participants with corneal deposits from slit lamp examination of the corneal epithelium.
- Time to onset of corneal deposits and overall time duration to resolution post treatment start.
- Time duration to resolution of corneal deposits after treatment cessation.
- Proportion of participants with new abnormalities compared with baseline observed with color retinal digital photography (conventional and wide field).
- Proportion of participants with new abnormalities compared with baseline observed with microperimetry.
- Proportion of participants with any new anomaly on the backlit ETDRS chart.
- Proportion of participants with any clinically significant change in ETDRS BCVA (defined as ≥ 15 letter change [≥ 3 lines] of change in ETDRS BCVA at 4 meters)
- Proportion of participants who develop a color deficiency using the FM-100 hue test.
- Proportion of participants who develop a loss of 0.12 or greater logCS on the Mars letter contrast sensitivity test.

- Proportion of participants who develop a psychiatric disorder in accordance with the DSM-5 as assessed with the M.I.N.I. 7.0.2 assessment questionnaire and suicidal ideation or suicide attempt by C-SSRS interview.
- Proportion of participants with an AE of dizziness or vertigo and severity as assessed by the DHI.
- Mean change from baseline in GTS, QOS, AFS, and BFW as assessed by the LSEQ.

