- Abnormality found on any of the following ophthalmologic examinations (only the test that revealed an abnormality will be repeated, unless at the discretion of the investigator additional testing is warranted):

- SD-OCT, qFAF, BCVA [ETDRS], FM-100 hue test, Mars letter contrast sensitivity test and M-chart.
- Slit lamp examination and digital photograph of corneal surface (cornea Verticillata) and retinal digital photograph (toxic maculopathy and retinopathy on conventional and wide field device).
- Microperimetry.

Participants will report to the Study Site in the morning.

The following assessments will be performed during this follow-up visit (if required):

- Blood sampling as needed to follow abnormality:
 - CBC and biochemistry;
 - MethHb %;
- Urine sampling as needed to follow abnormality:
 - Urinalysis (dipstick and urine microscopy if blood, leukocyte esterase, or nitrites are positive).
- Ophthalmic Assessments (repeat only if abnormal at Week 64). Abnormal results may need to be further investigated using microperimetry, color vision assessment with FM-100 hue test, Mars letter contrast sensitivity test and M-chart. Corneal deposits and retinal lesions from drug toxicity at Week 64 needed to be monitored by slit lamp examination, SD-OCT (including wide field macula scan), qFAF and photography (conventional and wide field);
- Psychiatric Assessment with M.I.N.I 7.0.2 (repeat if disorders are found at Week 64).
- Assessment with DHI (if participant reports ongoing AE of dizziness or vertigo).

General:

At all follow-up visits, participants will be reminded of the following before leaving the Study Site:

- Study restrictions as described in [Section 6.4](#);
- To return to the Study Site for the following scheduled visit; and
- To contact the Study Site in the interim should they experience AEs or require treatment with any concomitant medications.

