8.6. Assessment and Visit Windows

The following time-related windows will be acceptable based on logistical and operational considerations:

- Out Patient Week Visits: as follows, unless otherwise indicated by the investigator:
 - Week 4 \pm 3 days (Visit 3);
 - Week 12 \pm 2 weeks (Visit 4);
 - Week 24 \pm 2 weeks (Visit 5);
 - Week 52 \pm 2 weeks (Visit 6);

- Week 64 \pm 2 weeks (Visit 7a and 7b)

AND if ongoing AEs are being followed;

- Week 76 \pm 2 weeks (Visit 8).
- Week 89 \pm 2 weeks (Visit 9).
- Week 104 \pm 2 weeks (Visit 10).

At all-time points where multiple assessments are performed and blood samples are collected, vital signs measurements (when relevant) will be performed before blood sampling.

Any deviations from the above-mentioned permissible window periods will be documented as protocol non-compliances and will be evaluated for significance at the data review meeting prior to database lock.

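### Entry to Part 3 is defined in two incompatible ways, so observation of unresolved corneal deposits after Week 64 can depend on whether a site codes them as adverse events

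*Combined protocol and SAP*

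**What the plan says.** Two rules decide who is seen at Weeks 76, 89 and 104.

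AE-based wording:
- Section 5.1 (Part 2) and the Study Design row of the Synopsis: "If the participant has an ongoing AE, they will continue in Part 3 of the study, otherwise this is the final visit".
- Synopsis, Part 3 assessments: "visits will only be scheduled if an AE was ongoing at a prior visit".
- Section 1, Schedule of Events, column heading: "Phase 3 follow-up (ongoing AEs at end of Phase 2". The ophthalmic row under it is likewise tied to following an AE.
- Section 8.6, before the windows for Visits 8 to 10: "AND if ongoing AEs are being followed".
- The last bullet of Section 5.1 and the title of Section 8.5 also describe these visits as being for ongoing AEs.

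Abnormality-based wording:
- Section 5.1, duration paragraph: if abnormalities are found at Week 64, "the subject will continue quarterly follow-up out to 12 months post last dose of IMP". Its example is a participant whose only finding is a corneal deposit.
- Section 8.5 lists an ongoing AE as one criterion and, separately, "Abnormality found on any of the following ophthalmologic examinations (only the test that revealed an abnormality will be repeated". The examinations named include slit lamp and corneal photography.
- Section 9.2.6 makes the later eye examinations depend on ophthalmic abnormalities at Week 64 and repeats the deposit-only example.

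The stop rules differ too. Section 5.1 (Part 3) and the Synopsis design row have up to three further visits "or until resolution or stabilization of the AE whichever is earlier". The Synopsis Part 3 assessments run until resolution, within 12 months of the final dose. The duration paragraph of 5.1 runs to 12 months with no stabilization stop.

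The endpoint that relies on these visits is in Section 5.2.2: "Time duration to resolution of corneal deposits after treatment cessation". Section 12.2.3.2 assigns it a log-rank test and Cox regression.

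**The concern.** The two rules would be equivalent if every corneal deposit were an AE. The protocol does not make it one. Section 7.7 calls the deposits benign and without visual consequence. They are absent from the ophthalmic AEs of special interest in Section 10.11.1. That section counts an abnormal assessment as an AE when it is clinically significant, although it also lists a new sign, so an investigator could defend coding a deposit or leaving it uncoded. Participants are not told of deposits (Section 7.7), so they cannot report them. Coding practice has already differed within the programme: Section 2.1.1 and the Table 1 footnote say the Study 033 subgroup recorded deposits as AEs and Study 057 did not.

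A site following the AE-only wording would therefore release a participant with an unresolved, uncoded deposit at Week 64. For someone who completes dosing, that is the only scheduled eye examination after treatment and before Part 3. Time to resolution would reduce to resolved or not at about 12 weeks, with slower cases censored or kept according to coding habit. Those slower cases are the ones that would test, after 12 months of dosing, the statement in Sections 2.3.2 and 5.5.1.2 that deposits reverse within a year.

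**Working it through.** **Timeline.** Section 5.1 gives participation of up to 110 weeks.
- 6 weeks of screening + 104 study weeks = 110, which reproduces the stated figure.
- Stopping at Week 64 gives 6 + 52 + 12 = 70 weeks.
- Time off drug for a completer: 64 − 52 = 12 weeks at Week 64, and 104 − 52 = 52 weeks at Week 104.

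The 110 weeks therefore includes Part 3. It does not settle who enters, since either rule takes some participants to Week 104.

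**Same participant under each rule.** Take a completer with a corneal deposit at Week 64, no other finding, and no AE recorded.
- Part 2 sentence of 5.1, Synopsis, Schedule heading, 8.6: Week 64 is the final visit.
- Duration paragraph of 5.1, 8.5, 9.2.6: slit lamp and corneal photography continue at Weeks 76, 89 or 104.

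Both outcomes follow from current text, and Section 5.1 contains both.

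**Scale.** These figures are conditional. They assume the AE-only wording is applied literally, no deposit is coded as an AE, there is no dropout, and a 6-month study's rates carry over to 300 tafenoquine participants dosed for 12 months.

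Study 033 (Section 2.1.1.1): 69 of 74 on tafenoquine had deposits (93.2%), and 42 of the 69 had resolved 3 months after the prophylactic period.
- Unresolved: 69 − 42 = 27
- Share of deposit cases: 27/69 = 39.1%
- Share of those treated: 27/74 = 36.5%
- Applied to 300: 300 × 27/74 = 109

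Study 057 (Section 2.1.1.1): 15 new-onset cases on tafenoquine, reported as 21.4%, which implies 15/0.214 ≈ 70 treated. All but one resolved within 12 weeks of onset.
- Slow to resolve: 1/15 = 6.7% of cases, 1/70 = 1.4% of those treated
- Applied to 300: 300 × 1/70 = 4.3, about 4

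The Study 057 clock starts at onset, not at cessation, so 4 is only a rough lower marker for the number unresolved at Week 64. The Study 033 time point matches Week 64 more closely.

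**Other design figures.** Nothing here enters the sample-size or power calculation for the primary endpoint.

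**The case against.** The strongest reply is that the protocol plainly intends deposits to be followed. Three body sections provide for it, two with a deposit-only participant as the worked example. The Part 3 paragraph of 5.1, just after the AE-only sentence, refers to criteria for continuation, and 8.5 is where such criteria are listed. Section 10.11.2 also cites 8.5 as the source of the additional follow-up criteria. This stands. A reader of the Synopsis might infer that uncoded deposits are never followed after Week 64; the documents do not support that.

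A reader might also infer that Section 5.2.2 contradicts Section 5.1. It does not: it lists an endpoint and sets no follow-up rule. The endpoint depends on whichever rule a site applies.

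On stopping, one can argue that the stabilization wording concerns AEs, so it cannot affect an uncoded deposit. That is right for uncoded deposits, where the problem is entry. For coded deposits entry is secure and the stop rule is the problem, so different participants are affected. Section 10.11.2 joins the two by taking entry from 8.5 and stopping when the AE resolves or stabilizes.

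A reader might further infer that participants who stop drug early lose observation, because Part 3 visits are fixed by study week. Section 5.1 keeps them on all scheduled visits. Someone whose last dose was at Week 20 is examined at Weeks 24, 52 and 64, which is 4, 32 and 44 weeks later and more off-drug observation by Week 64 than a completer has.

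Finally, site coding is unknown and the upper figure needs every site to disregard three sections. That also stands: 109 is a bound under stated assumptions, not a forecast.

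**Conclusion.** The inconsistency is real and should be corrected. Part 3 entry is worded as AE-only in the Synopsis, the Schedule of Events, the Part 2 sentence and last bullet of 5.1, and 8.6. The duration paragraph of 5.1, 8.5 and 9.2.6 word it as any ophthalmic abnormality at Week 64. The rules separate participants with unresolved deposits that were not coded as AEs, and so bear on one secondary safety endpoint.

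The range is about 4 to 109 of 300 tafenoquine participants, and only under the assumptions in the working. The likely effect cannot be estimated, because it depends on which wording sites follow and how they code deposits. Combining one prior study's deposit incidence with the other's unresolved fraction would give a figure that neither study supports. The primary endpoint, its margin and its power are unaffected.

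**What to change.** Reconcile all the listed passages to one Part 3 entry criterion: both Synopsis statements, the Schedule heading and its ophthalmic row, the Part 2 sentence and last bullet of 5.1, the title of 8.5, and 8.6. For observing the resolution endpoint, cite the criteria list in 8.5, to which 5.1 and 10.11.2 already point. Deposit-only participants would then have the slit-lamp and corneal photography visits already planned in 5.1 and 9.2.6.

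Reconcile the three stop statements (resolution or stabilization, resolution, and 12 months after last dose), together with 10.11.2, so that a stable but unresolved deposit is not dropped from endpoint observation. State in the analysis section how a deposit still unresolved at the last examination is censored. All of this concerns data collection for a listed endpoint; what clinical follow-up a participant needs remains for the sponsor and investigators.

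The cost is wording in more than three places and more short Part 3 eye visits than under the AE-only reading. No new type of assessment or visit week is needed.
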